Exclusion Criteria: The following characteristics exclude potential participants from being randomized into the study: DSM-IV* diagnosis of an uncontrolled psychiatric disorder with psychotic symptoms or cognitive impairment; if taking psychiatric medication, **NOT** on a stable dose for at least 30 days prior to randomization; any suicidal ideation in the past 7 days, plan or intent past 6 months, or suicide attempt past year; homicidal ideation with plan and intent in the past 30 days; PHQ-9 endorsement of hopelessness or self-harm/SI and/or sum score ≥ 19 on items 1-9; any use of prazosin or naltrexone past 30 days; currently taking disulfiram or acamprosate OR planning to take any of these medications (including prazosin or naltrexone) during the 8 weeks of the study; current moderate or greater level of substance use disorder (past 30 days) on any psychoactive substance other than alcohol, nicotine, or cannabis; current diagnosis of any opioid or amphetamine use disorder, OR use of any amphetamine or opioid-containing medications during the previous 30 days; UDA screen positive for amphetamine, opioids; significant acute or chronic medical illness including unstable angina, recent myocardial infarction, history of congestive heart failure, preexisting hypotension (sys <100) or orthostatic hypotension (sys drop of > 20 mmHq; after two minutes of standing, or any drop w/dizziness): insulin-dependent diabetes mellitus: chronic renal or hepatic failure; pancreatitis; Meniere's disease; benign positional vertigo or narcolepsy; liver enzymes aspartate aminotransferase (AST), cirrhosis, alanine aminotransferase (ALT), gamma glutamyl transferase (GGT), > 8 x the upper limit of normal or total bilirubin >2 mg/dL (in the absence of Gilbert's disease); allergy or previous adverse reaction to naltrexone, prazosin, quinazolines, or other α -1 adrenergic blockers or use of other α -1 adrenergic blocker; women who are pregnant, breastfeeding, or of childbearing potential and not using a contraceptive method judged by the investigator to be effective; legal involvement that could interfere with study participation including being court ordered for treatment; signs or symptoms of withdrawal at time of initial consent, or any participation in an experimental drug study or any addiction study past 30 days (See Appendix 1 for Initial Inclusion/Exclusion Checklist).

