Screening Procedures: The Study Clinician administers the substance use disorders section of the Mini International Neuropsychiatric Interview (MINI) to confirm DSM-V AUD and to assess for other potential substance use disorder diagnoses, any suicidal ideation in the past 7 days, plan or intent past 6 months, or suicide attempt past year, and homicidal ideation with plan and intent in the past 30 days (see *Study Instruments Table* below for an overview of assessment measures and materials). Recent drinking will be determined during the AUD assessment to determine whether participants meet drinking inclusion requirements. Presence of at least mild craving will be assessed via the self-report instrument "Pennsylvania Alcohol Craving Scale (PACS);" a score of at least 10 is required. Participants undergo a complete medical history and a physical examination with the Study Clinician. Participants who are found to be in good medical health from the initial exam complete the Clinician-Administered PTSD Scale for DSM-5 (CAPS) —to determine current PTSD diagnostic status. Participants complete a self-report demographic questionnaire that includes a forced choice item regarding their goals for their alcohol use over the next month (i.e., no change, reduce or cut down on amount of drinking, abstain completely). Those who indicate no desire to change their drinking are excluded from the study.

Those who are found to be initially eligible are asked to complete a short battery of self-report measures regarding craving, PTSD symptom severity, and characteristics that may moderate response to prazosin and naltrexone.

Data Capture: The interview data are recorded on paper or entered directly into an ACCESS database and self-report measures are entered online into a Survey Monkey form. Research staff remain in the room with participants while they complete the self-report measures to ensure that they do not leave the Survey Monkey website. Note: there are paper forms available in the event there is a problem with either the ACCESS or Survey Monkey systems or if a participant prefers to complete measures off-line.

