Laboratory Procedures: Women of childbearing potential provide urine for a pregnancy test at screening and again at weeks 4 and 8. Laboratory evaluation of blood samples includes CBC, routine liver function tests, and routine serum chemistries. Specimens are also sent to a lab in Minnesota, MedTox, for assessment of the alcohol biomarker phosphatidylethanol – Peth. The lab procedure differs slightly by site as follows: Seattle VA: The Clinical Research Unit (CRU) draws the blood samples and ship the specimens to MedTox. Either the Clinical Research Unit (CRU) or study staff deliver the remaining vial(s) to the Seattle VA lab for processing. Study participants are escorted by study staff to the CRU at the end of the initial study visit.

American Lake VA: Clinical Studies Unit staff (CSU) draws the blood samples and ships the specimens to MedTox. A member of the Clinical Studies Unit (CSU) or study staff delivers the remaining vial(s) to the lab for processing. Study participants are escorted by study staff to a room in the CSU at the end of the initial study visit.

Mt. Vernon CBOC VA:Blood specimens are drawn by lab personnel in the on-site lab. Specimens are then transported to the Seattle VA via a courier service. Mt Vernon CBOC VA specimens for MedTox are held at an identified location in the Seattle VA lab and then picked up by Clinical Research Unit (CRU) staff to be shipped to MedTox.

Safety and Comfort Call by Study RA (Safety and & Comfort Call #1): The RC calls the participant the next business day following the initial screen to assess any symptom exacerbation stemming from the visit, to provide support.

Randomization, Baseline Assessment, and Initial Medication Administration (Visit 2; Study Day 8):

Randomization: In this double-blind, double-dummy design participants are randomized to one of four study conditions: prazosin + naltrexone; prazosin + naltrexone placebo; naltrexone + prazosin placebo, and double placebo. Randomization is blocked by gender, PTSD status, and alcohol consumption goal (abstention vs. reduction). Random assignment to study condition is conducted by the VAPSHCS Research Pharmacist with randomization tables supplied by the study PIs. The Research Pharmacist distributes study medications appropriate to the randomization condition. The Research Pharmacist will have no contact with participants. Study medications will have been prepared ahead of time and will be available at Study Visit 2.

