Baseline Assessment: Approximately one week after the screening visit (Study Day 8) the RC or Study Clinician contacts each participant to inform her/him as to whether she/he continues to fit the study inclusion criteria. Note: If issues arise while attempting to contact participant, there may be up to an additional week between the initial screen and the baseline appointment. At the outset of this visit, blood pressure and suicidality are rescreened to ensure that participants are safe to start the study medications. Those that are eligible and wish to continue are asked to complete the Form-90 to evaluate drinking history over the past three months. They also complete the Script Preparation Form to provide details for the craving induction paradigm (see below). They also complete a battery of self-report measures as well as complete the two craving measures (Desire for Alcohol Questionnaire and Obsessive Compulsive Drinking Scale) again.

Form-90 Details. The RC or Study Clinician administers the Form-90 to ascertain drinking history over the last three months as well as involvement in various types of health care and mental health treatment.

Script Preparation Details. Participants complete the Script Preparation Form to provide details regarding two different recent situations that led to alcohol craving or actual use, including physiological and emotional reactions and specific information on the type of alcohol craved or consumed. One situation will have evoked anxiety, concern, or worry that led to craving or consumption, and the other will have involved craving or consumption meant to lead to or enhance positive emotional reactions in a situation or that pertain to desired effects of alcohol (e.g., feeling high, intoxicated, "good," etc.). These materials are used by study staff to write brief, personalized, imaginal craving inductions using a standard format that portrays each experience in the second person, present tense, and incorporates between five and seven different visceral and muscular reactions. The imaginal scene leads the person through the situation up to the acquisition of the alcohol and bringing the drink to her/his lips (but not consuming it). Each induction is 1 minute long (approximately 214 words) and is recorded in a neutral tone by someone other than the Study Clinician or RC for replay during the induction procedures at session 8

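### The planned-medication exclusion leaves out opioids, so a person with a foreseeable opioid course can be randomised to blinded naltrexone

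*Combined protocol and SAP*

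**What the plan says.** The Exclusion Criteria contain one medication rule that looks ahead. It excludes anyone "currently taking disulfiram or acamprosate OR planning to take any of these medications (including prazosin or naltrexone) during the 8 weeks of the study". Opioids are handled in later clauses, by three criteria:

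- past use: "use of any amphetamine or opioid-containing medications during the previous 30 days";
- current disorder: "current diagnosis of any opioid or amphetamine use disorder";
- urine test: "UDA screen positive for amphetamine, opioids".

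At Visit 1, under Screening Procedures, "Participants undergo a complete medical history and a physical examination with the Study Clinician". About a week later, under Baseline Assessment, staff contact is made that "contacts each participant to inform her/him as to whether she/he continues to fit the study inclusion criteria". That section names blood pressure and suicidality as the items re-screened at Visit 2. On supply, the Randomization paragraph states: "Study medications will have been prepared ahead of time and will be available at Study Visit 2".

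Under Medication Administration, naltrexone or its placebo is taken at 50 mg from dosing Day 1 through Day 42 with no titration. Participants also receive a card warning emergency staff that they may be on naltrexone if opioid pain relief is needed.

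**The concern.** The protocol regards naltrexone together with opioids as a conflict. That is visible in the three opioid exclusions and in the alert card. It also contains a ready-made form of words for excluding planned medication. The two are not joined: the planning clause does not name the one drug class that the card warns about.

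An elective opioid course is often known in advance. If it is not picked up before randomisation, it comes to light when the participant is already taking blinded capsules. The choices are then to stop study drug, break the blind or change the participant's pain care. What is at stake is mainly participant safety, and a discontinuation or unblinding that could have been foreseen.

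**Working it through.** No published figure needs reproducing. The check is a comparison of the printed rules, plus a small timing calculation.

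**Step 1: direction of each rule (Exclusion Criteria).**

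- Drugs named in the planning clause: disulfiram, acamprosate, prazosin, naltrexone = 4.
- Opioid criteria on past or current status: recent use, current disorder, positive urine screen = 3.
- Opioid criteria on planned use = 0.

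The planning clause cannot be read to include opioids. Its reference to these medications points back to disulfiram and acamprosate, with prazosin and naltrexone added in parentheses. Opioids first appear in a later clause.

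**Step 2: timing.** Inputs: Visit 1 is study Day 1. Visit 2 is Day 8, with up to one further week allowed (Baseline Assessment), so Day 15 at the latest. Dosing runs 42 days (titration table). Assume that the first dose is taken on the evening of Visit 2.

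- Dosing on time: study Days 8 to 8 + 41 = 49.
- Dosing after the maximum delay: study Days 15 to 15 + 41 = 56.
- Whether the opioid look-back is counted to Visit 1 or to randomisation, it ends before the first dose. Dosing days covered: 0 of 42.
- Planning clause: 8 × 7 = 56 days. Counted from Visit 1, it ends on Day 56, so it would reach the last dosing day in both cases if it named opioids.

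**Step 3: a worked case.** Take an otherwise eligible person with surgery and post-operative opioids booked for study week 4 (Days 22 to 28). If Visit 2 is on Day 8, this is dosing days 22 − 7 = 15 to 28 − 7 = 21. If Visit 2 is on Day 15, it is dosing days 22 − 14 = 8 to 28 − 14 = 14. At entry this person has no opioid use in the past 30 days, no opioid use disorder and a negative screen, and plans to take none of the four named drugs. No printed criterion excludes the person on this ground. Naltrexone is in 2 of 4 conditions, so the chance of active drug is one half if allocation is equal. That is an assumption, since no ratio is printed.

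**Step 4: does anything printed later close the gap?**

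- The medical history may reveal the surgery, but no criterion then requires exclusion.
- The general-health criterion (Inclusion) and the acute or chronic illness criterion (Exclusion) do not mention planned procedures or planned opioid treatment. A healthy person can have elective surgery.
- The further condition for randomisation in the text (Additional Inclusion/Exclusion Criteria) concerns laboratory values.
- The safety review and alert card come when drug is dispensed, after assignment, and the card is for emergencies.
- Visits and calls during dosing use an open question about how the participant has felt, with no named question on new or planned medication.
- Stopping drug and breaking the blind are responses after exposure.

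**The case against.** The strongest reply has four parts.

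First, the operative forms are not in the text. The Exclusion Criteria and the Additional Criteria both refer to Appendix 1 checklists, which may ask about planned opioid use. This stands as a limit: the point is about the criterion as printed, and a reader should not infer that nobody asks.

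Second, the planning clause names the study drugs and other alcohol medications, so its purpose may be to avoid overlapping treatment rather than to protect against opioids. That is a fair reading of why it was written. It does not supply an opioid rule elsewhere.

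Third, clinical judgement narrows the gap. Records are reviewed before letters go to Veterans found through the database, a clinician takes a full history, and medication precautions are reviewed at dispensing. These would catch some cases, but none obliges the clinician to exclude, and there are three sites.

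Fourth, the consequences are limited. The Design Overview says both drugs can be stopped safely without tapering, and a planned course leaves time to stop the capsules without unblinding. Drinking outcomes come from the Form-90 interview and the analysis is intent-to-treat. This part stands. A reader might infer that affected participants are lost to the primary analysis, but the documents do not show that. Discontinuation is paired with ending participation only for blood-pressure side effects, as clinically appropriate.

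A reader might also infer a general failure to re-check medication between Visit 1 and randomisation, for instance because psychiatric medication must be "on a stable dose for at least 30 days prior to randomization" and Visit 1 falls earlier. The text does not support this. That criterion is already timed to randomisation, only people still eligible continue at Visit 2, and the additional checklist is unseen.

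**Conclusion.** The point holds as a gap in the printed eligibility criteria. Opioid-containing medication is barred on past or current status only, and a person with a foreseeable opioid course in the dosing weeks may be randomised to blinded naltrexone at full dose. The protocol's own provisions are enough to show that this is a hazard.

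The size can be given only structurally: 0 of 3 opioid criteria look ahead, 0 of 42 dosing days are covered, and 2 of 4 arms are exposed. The documents give no rate of planned opioid courses, so no count of affected participants is offered. No primary estimate or test is shown to be affected. The conclusion rests on the printed text and would reduce to a wording mismatch if the Appendix 1 checklists already contain the question. With that limit, the change should be made, because it alters who may be randomised and is more than missing detail.

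**What to change.** Extend the planning clause so that it also excludes anyone planning to take, or expected to need, opioid-containing medication during the 8 weeks of the study. Ask about this at Visit 1 and again at the existing eligibility contact near Day 8. Do not randomise anyone who then meets the criterion. If the Appendix 1 checklists already ask, align the wording of the Exclusion Criteria with them.

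Order matters. Study drug is prepared before Visit 2, so the second question must be answered before the pharmacist assigns a condition. Otherwise an exclusion becomes a post-assignment loss in an intent-to-treat trial of 120.

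The cost is one clause and a brief question at two contacts that already exist, with no new visit or test. The downside is a small number of extra screen failures, at a rate the documents do not give. On the protocol's own planning figures, each replacement randomised would need about 1500 / 120 = 12.5 telephone screens.

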Self-report Details. In addition, participants complete self-report measures on craving, drinking motives, and social networks. In addition, potential phenotypic moderators of interest will be examined, including family history of AUD, age of onset of drinking and AUD, drinking motives, depression, PTSD severity, anxiety sensitivity, emotional reactivity, disinhibition/impulsivity, and sensitivity to reward and punishment. They also complete the Stroop, another measure of impulsivity, which is administered by the RC or Study Clinician.

Medication Administration: Upon completion of the questionnaires the Study Clinician meets with the participant and orients him/her to the medication regimen. A two-week supply of the study medications loaded into a 14-day, 3-compartment Mediset is provided along with written instructions with visuals (i.e., pictures of the capsules) regarding dosing. Safety precautions regarding the medications are reviewed and participants are reminded to call the study telephone number should they experience any concerning side-effects or have any questions. The two-week prazosin titration schedule detailed in Table 1 is followed. Naltrexone does not require a titration period; participants are instructed to take the naltrexone/matched placebo capsule at the 9pm dosing time. Participants are given a pre-printed index-size card with study contact information and an alert that they could be taking naltrexone should they need emergency medical care involving pain medication (i.e., opiates).

Titration Schedule

ili alion Scriedule.				
Prazosin	9 AM	3 PM	9 PM	Naltrexone 9 PM
Dosing:				Dosing:
Days 1-2			1 mg	50mg
Days 3-4	1 mg	1 mg	1 mg	50mg
Days 5-7	2 mg	2 mg	2 mg	50mg
Day 8-10	2 mg	2 mg	8 mg	50mg
Day 11-14	4 mg	4 mg	8 mg	50mg
Day 15-42	4 mg	4 mg	8 mg	50mg

Study Clinician Safety and Comfort Call (Safety and Comfort Call #2): The Study Clinician calls each participant the day immediately following the initial dose of study medications to assess whether any concerning side effects were experienced, including any suicidal ideation.

Vital Signs and Adverse Events Checks (Visits 3-7; Safety Calls # 3 & 4):

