In-person Visits: To assure that participants are tolerating the study medications they are scheduled for five brief visits after the initial medication administration visit and before the final visit. Study days 12, 19, 29, 36, and 42 are the target (± 3 days) days for these in-person visits. At each of the in-person visits, sitting and orthostatic BP and HR are obtained. Participants are queried for adverse events using the open-ended question "How have you been feeling since you were last here?" Any elicited adverse events are recorded and rated for severity, duration, action taken, and relatedness to study medication. 20 mmHg drop in systolic BP accompanied by dizziness, lightheadedness or syncope at time of measurement or blood pressure systolic reading <100 with reported dizziness, lightheadedness or syncope at the time of measurement or between visits are considered unacceptable side effects and the titration is slowed or decreased to the last tolerated dosage or medication discontinued and study participation terminated as clinically appropriate. When the titration is adjusted, new study medications are requested from the pharmacy immediately and dispensed before the participant leaves.

In addition, participants complete a brief battery of measures to assess depression, anxiety, pain, and sleep and wake disturbance at each in-person visit. Participants are administered the PHQ-9 to screen for depression and suicidal ideation; the PHQ-9 was adapted for a one week timeframe.

Safety Calls: Study days 16 and 22 will be the target (± 3 days) days for the telephone calls 2 and 3. Participants are queried for adverse events using the open-ended question "How have you been feeling since we last saw you in the research clinic?" If safety concerns are apparent, participants are either be told to discontinue study medications or to adjust their dosing. An in-person study visit is scheduled as soon as possible in either case. The PHQ-9 suicide screen question is asked during each call with the timeframe adapted to cover since the participant last had contact with study staff.

Final Assessment and Craving Induction (Visit 8; Study day 42):

Final Visit Timing: Participants are scheduled to come back for their final visit approximately 7 weeks after their screening visit (Note: if scheduling difficulties arise there may be up to a two-week delay following the target end of the medication period in completing the final visit).

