provocative reading material and puzzle books prior to completing the second induction, the procedures of which parallels the first.

Study Medications

Prazosin: Prazosin HCl or identical matched placebo capsules are dispensed as 1, 2, and 4 mg capsules prepared by Kelley-Ross Pharmacy, a compounding pharmacy in Seattle. A 25mg riboflavin trace will be added to each capsule to evaluate medication compliance.

Naltrexone: 50 mg naltrexone or identical matched placebo capsules prepared by Kelley-Ross Pharmacy (tablets are ground and then compounded with the 25mg riboflavin trace).

Procedures for Maximizing Research Integrity

Maintaining the Study Blind: Only the VAPSHCS research pharmacist will have access to the randomization schedule, and she will have no contact with study participants. The blind may be broken by the PIs in case of safety concerns and for the purposes of interim analyses, but the information will not be shared with study staff except in the event of clinically significant safety concerns.

Maximizing Retention: We update contact information at each clinical and assessment visit. Participants will be paid \$15 for each of the two blood draws.

Study Instruments

Study Construct/ Variables	Study Phase	Purpose
Inclusion/Exclusion Criteria and Blocking Factors		
Demographic information	V1	sample description, blocking (gender)
Medical history interview	V1	exclusion
Medical Exam	V1, V8	exclusion; safety
Lab values MINI International Psychiatric Interview (DSM-V AUD & SUD onset of drinking and alcohol problems as well as recent drinking; DSM-IV Psychosis; suicidality, homicidality)	V1, V8 V1	exclusion; safety inclusion and exclusion
Alcohol use goal (embedded in MINI AUD)	V1	inclusion, blocking, treatment moderator
Desires for Alcohol Questionnaire (DAQ)	V2, V8	, outcome
Life Events Checklist	V1, V8	blocking
Penn Alcohol Craving Scale	V1, V2, V8	inclusion
Clinician-Administered PTSD Scale For DSM-5 (CAPS)	V1, V8	blocking, treatment moderator (Aim 3)
Tracking		
Contact form	V1-V7	retention
Primary Outcomes		
Alcohol Biomarker (Peth)	V1, V8	outcome
Alcohol Craving (DAQ)	V8	outcome (Aim 2)
Alcoholuse	V8	outcome (Aim 2)
Reward Craving for Craving Inductions from DAQ	V8	outcome (Aim 1)
Relief Craving for Craving Inductions from DAQ	V8	outcome (Aim 1)
Hypothesized Moderators		
State Trait Anxiety	V1, V8	moderation (Aim 3)
Anxiety Sensitivity Inventory	V1, V8	moderation (Aim 3)

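### The participant emergency card, as described, warns of possible naltrexone but not of possible prazosin, which two of the four blinded arms take

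*Combined protocol and SAP*

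**What the plan says.** The Medication Administration paragraph for Visit 2 describes "a pre-printed index-size card with study contact information and an alert that they could be taking naltrexone". The rest of that sentence gives the purpose: emergency care in which opiate pain medication might be used. No other section describes the card, and none mentions a carried alert for prazosin.

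The Randomization section says participants are "randomized to one of four study conditions: prazosin + naltrexone; prazosin + naltrexone placebo; naltrexone + prazosin placebo, and double placebo". Prazosin is therefore active in two arms of four, and so is naltrexone. Because the trial is double-blind and double-dummy, any participant might be on either drug.

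On how the drugs reach the participant:

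- **Study Medications:** "Prazosin HCl or identical matched placebo capsules are dispensed as 1, 2, and 4 mg capsules".
- **Medication Administration:** "A two-week supply of the study medications loaded into a 14-day, 3-compartment Mediset is provided", along with written, illustrated dosing instructions.

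On the hazards watched for during treatment:

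- **In-person Visits (Visits 3-7):** one trigger is a "20 mmHg drop in systolic BP accompanied by dizziness, lightheadedness or syncope at time of measurement". The other is a systolic reading below 100 "with reported dizziness, lightheadedness or syncope at the time of measurement or between visits are considered unacceptable side effects".
- **Safety Calls:** a non-numeric rule applies. "If safety concerns are apparent, participants are either be told to discontinue study medications or to adjust their dosing".
- **Exclusion Criteria:** at entry the protocol excludes "use of other α -1 adrenergic blocker".

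**The concern.** The card is the only item the protocol describes as carrying an alert for emergency care. As described, it names one of the two drugs the bearer may be taking, and a clinician could read it as the full list.

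The drug left out is the one most closely tied to the hazard the protocol monitors most concretely. Blood pressure supplies the only numeric on-treatment triggers, and the below-100 trigger extends to symptoms between visits. The plan thus expects that dizziness or fainting may occur away from study staff.

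At stake is a piece of safety information. Suppose a participant faints, or has a low reading, in front of a clinician outside the study, and does not mention prazosin. Until that clinician calls the study, nothing on the card as described points to a possible alpha-1 blocker.

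**Working it through.** There is no plan figure to reproduce. The check sets the relevant sections side by side and counts the people concerned.

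**1. What the card is said to carry.** Medication Administration (Visit 2) lists study contact information and the naltrexone alert. Prazosin is not listed there, and no other section adds it.

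**2. Whether something else the participant has would identify prazosin.**

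- Capsules: compounded, and matched to placebo (Study Medications).
- Container: a 14-day Mediset. No drug-name label on it is described.
- Written dosing instructions: these may name prazosin, but they are not described as something the participant carries.

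**3. Dose and timing.** The target daily dose is 4 + 4 + 8 = 16 mg (Design Overview and the titration schedule). The 9 PM dose rises from 2 mg to 8 mg on medication day 8. If medication day 1 is study day 8, the day given for Visit 2, that step falls on study day 8 + 7 = 15. The nearest target in-person visits are days 12 and 19, with a target phone call on day 16. The evening of the step-up is therefore spent at home. The call partly covers it, but cannot inform an outside clinician that same night.

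**4. How many participants.** The planned number randomized is 120. No allocation ratio is stated, so equal allocation is assumed.

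| Group | Formula | Equal allocation | If each arm holds 20% to 30% |
|---|---|---|---|
| Taking prazosin (two arms) | 120 × 2/4 | 60 | 120 × 0.40 = 48 to 120 × 0.60 = 72 |
| Prazosin with naltrexone placebo (one arm) | 120 × 1/4 | 30 | 120 × 0.20 = 24 to 120 × 0.30 = 36 |

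For the second group, the only drug the card is described as naming is one they are not taking. The 20% to 30% range is illustrative and has no source in the documents.

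**5. What cannot be computed.** The documents give no rate of fainting and no rate of outside emergency care. The figures above are numbers exposed to the gap, not expected events.

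**The case against.** The strongest objection is that the point rests on silence about a card that is not in the documents. One sentence describes it, and that sentence does not say that naltrexone is the only drug named. This stands. The finding concerns the card as described, and the first step must be to look at the printed one.

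Second, the alert has a stated and sound purpose, the conflict between naltrexone and opiate pain relief, and was not offered as a list of study drugs. The documents name no comparable conflict between prazosin and emergency treatment. This also stands: the scenario of an uninformed clinician is an inference, and the opiate alert should stay. It does not change the fact that the card would be silent on a drug the bearer may be taking.

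Third, there are many other safeguards:

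- Hypotension and orthostatic hypotension are excluded at entry.
- Participants must pass a consent comprehension quiz.
- Blood pressure is rechecked before the first dose, and sitting and orthostatic readings are taken at each in-person visit.
- Prazosin starts at a single 1 mg evening dose and is titrated over two weeks.
- Precautions are reviewed, participants are told to call about side effects, and safety calls are made.
- The principal investigators may unblind for safety, a research monitor can intervene, and clinical backup exists at the sites.
- The card carries the study's contact details.

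These are real and make the residual risk small. They either lower the chance of an event or work through the study team or a participant able to report. None tells an outside clinician about prazosin before that clinician has called.

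Finally, the counts measure exposure and not risk, and a conditional alert for naltrexone is equally inapplicable to the double-placebo arm. Both remarks are fair, and for that reason no event count is claimed.

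**Conclusion.** The concern holds as a minor point. The card as described alerts outside clinicians to possible naltrexone only, while half the participants (60 of 120 under assumed equal allocation; 48 to 72 if arms hold 20% to 30% each) would be taking prazosin. The gap is narrow: it matters only when an outside clinician sees hypotension or a faint, has not yet contacted the study, and is not told about prazosin. How often that would happen, and whether care would differ, cannot be judged from the documents.

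The conclusion assumes that the printed card matches its description. Confidence is moderate for that reason. No outcome, estimand or analysis is affected.

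**What to change.** Check the printed card. If it already names prazosin, only the protocol sentence needs to be brought into line.

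If prazosin is absent, put the following on every card, and the same content in the Medication Administration sentence:

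> The bearer is in a blinded trial and may be taking prazosin (an alpha-1 blocker), naltrexone, both or neither.

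Keep the contact details and the opiate alert. Dosing, visits and monitoring stay as they are.

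The cost is a card reprint, one protocol sentence and notification of the IRB. The blind is not affected: the wording is the same for all participants and, like the existing naltrexone alert, says only what the bearer might be taking.
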